7.3 Summary of Novexatin Non-Clinical Studies

From *in vitro* antifungal susceptibility studies novexatin exhibited dose-dependent fungicidal activity (median MIC₉₀ of 1 mM) and killed *Trichopyton* spp. via membranolysis within 3 hours of exposure in infected nail fragments.¹³ Treatment with Novexatin 10% for 28 days

A Randomized, Placebo-Controlled, Double-Blind, Parallel-Group, Multi-Site Phase 2b Clinical Study to Assess the Efficacy, Safety and Tolerability of 8-Week Regimens of Novexatin®, 10% Topical Solution (Taro Pharmaceuticals, USA, Inc.) in Patients with Mild to Moderate Onychomycosis

cleared quantifiable fungi in infected nail fragments and eradicated fungal growth in an *ex vivo* full thickness human toenail model.¹³

Single and repeated-dose toxicology studies by the intravenous, oral and dermal routes of administration have been performed with novexatin.¹⁴ No signs of local or systemic toxicity were seen in minipigs during repeated-dose dermal toxicology studies with up to 50 mg/kg/day of novexatin (> 10X proposed clinical dose) topically applied in the proposed clinical formulation. The dermal no-observed-adverse-effect level (NOAEL) was 50 mg/kg/day.¹⁴ Acute toxicity studies with intravenous doses of novexatin in rats and dogs identified the maximum tolerated dose (MTD) to be 2 mg/kg/day with the no observed adverse effect level (NOAEL) of 0.5 mg/kg/day in male rats and 1.25 mg/kg/day in female rats.¹⁴ In rats, toxicological signs seen at higher doses included transient signs such as abnormal respiration, subdued behavior, hunched posture, body held low, and rolling gait. Histopathology examination identified signs of kidney tubule regeneration in some animals dosed above the NOAEL. In a mouse study to investigate the potential oral toxicity mediated by a single dose of novexatin in the proposed clinical formulation an MTD of approximately 260 mg/kg was identified.¹⁴ The toxicological profile of the D- and L-enantiomers is equivalent and their bioactivity is identical.¹²

Toxicokinetic evaluations in the repeat studies showed no quantifiable plasma concentrations of novexatin in the minipig dermal administration study.^{12,14} Plasma data from the intravenous rat repeated-dose study showed a terminal plasma half-life (t_{1/2}) of approximately 3-6 hours.^{12,14}

An *ex vivo* study showed an average 3.53% of the radiolabelled novexatin applied to the surface of the nail was able to penetrate deep into the nail plate of uncompromised (i.e., by infection) intact full-thickness human nail.

In a human skin penetration study, novexatin absorption was minimal, accounting for 0.01% of the applied dose.¹² This low systemic exposure was also observed in dermal sensitization studies where the systemic exposure was below the lower limit of quantification (LLOQ) of the bioanalytical assay employed to monitor serum levels. Owing to the minimal systemic exposure seen from *in vitro* and *in vivo* dermal studies, major organ systems are not expected to be exposed to measurable levels of novexatin.

Details of the results of the non-clinical studies are provided in the Novexatin Investigator's Brochure.¹²

In a 60-Day Dermal (Semi-Occluded) Toxicity Study in the Minipig with a 14-Day Treatment-Free Period novexatin in a new formulation, administered by dermal application daily to the back for at least 60 consecutive days to the minipig, at concentrations of 5 % and 10 % was well tolerated. There was no evidence of either local or systemic target organ toxicity after the treatment period.

A Randomized, Placebo-Controlled, Double-Blind, Parallel-Group, Multi-Site Phase 2b Clinical Study to Assess the Efficacy, Safety and Tolerability of 8-Week Regimens of Novexatin®, 10% Topical Solution (Taro Pharmaceuticals, USA, Inc.) in Patients with Mild to Moderate Onychomycosis

7.4 Summary of Novexatin Clinical Studies

In Phase I/IIa studies with topical administration of Novexatin (referred to as a 9.3% solution representing 93 mg/mL of the L-configuration, equivalent to the current 10% solution) in 40 otherwise healthy patients with mild-moderate fungal infection of the toenail(s) on no current topical or systemic antifungal therapy showed a low incidence of adverse events (AEs).¹² AEs judged possibly related to study product were limited to application site reaction and headache. For AEs overall and for the events judged possibly related, the incidences among Novexatin- and placebo-treated patients were similar. Plasma concentrations of novexatin were below the lower limit of quantitation of the enzyme-linked immunosorbent assay (ELISA).¹²

In a Phase I study the systemic exposure and pharmacokinetics of novexatin in a new formulation was determined after repeated once-daily topical application of Novexatin solution, 10% in a maximal-use setting in adult patients with distal subungual onychomycosis of the toenails and in healthy adult subjects without onychomycosis. Safety was assessed through the evaluation of changes from pre-dose in physical examination findings, vital signs, clinical laboratory findings, 12-lead ECGs and by the occurrence of adverse events (type, frequency, severity) and premature discontinuations from study.

The results of this *An Open-Label, Multiple-Dose, Safety and Pharmacokinetic Study of Novexatin® Solution, 10% in Healthy Adult Volunteers and in Patients with Severe Distal Subungual Onychomycosis* study demonstrate that Novexatin solution 10% is safe and plasma concentrations of novexatin were below the lower limit of quantitation of the enzyme-linked immunosorbent assay (ELISA) following 28-day maximum-use once-daily topical doses in healthy subjects and patients with severe DSO.

8.0 STUDY OBJECTIVES

1. Determine the rates of complete therapeutic cure of Novexatin® 10% topical solution (Taro Pharmaceuticals, USA) after daily dosing for one 8-week treatment period (Treatment Group A) and two 8-week treatment periods separated by a 32-week rest period (Treatment Group

A Randomized, Placebo-Controlled, Double-Blind, Parallel-Group, Multi-Site Phase 2b Clinical Study to Assess the Efficacy, Safety and Tolerability of 8-Week Regimens of Novexatin®, 10% Topical Solution (Taro Pharmaceuticals, USA, Inc.) in Patients with Mild to Moderate Onychomycosis

B), and Placebo (vehicle) topical solution (Taro Pharmaceuticals, USA) after two 8-week treatment periods separated by a 32-week rest period (Treatment Group C), at three test-of-cure visits conducted at Day 141, Day 281 and Day 365 in patients with mild to moderate distal subungual onychomycosis of the target toenail.

2. Compare rates of complete therapeutic cure between Treatment Groups according to a hierarchical evaluation scheme detailed in the statistical sections.
3. Evaluate safety and tolerability of the two regimens of Novexatin® 10% topical solution (Treatment Groups A and B) in patients with mild to moderate distal subungual onychomycosis of the target toenail.

9.0 INVESTIGATIONAL PLAN

9.1 Study Design and Plan Description

This randomized, placebo-controlled, double-blind, parallel-group, multi-site study is designed to evaluate and compare the efficacy and safety of two dosing regimens of Novexatin® 10% topical solution (Taro Pharmaceuticals USA) for the treatment of mild to moderate distal subungual onychomycosis of the target toenail. Additionally the active formulation in these regimens will be assessed for superiority to a placebo topical solution.

Up to 180 eligible patients with distal subungual onychomycosis who meet all the inclusion criteria and none of the exclusion criteria will be enrolled into the study at Visit 1. Patients must be at least 18 years of age, in overall good health. They should have a current diagnosis of distal subungual onychomycosis of mild-moderate severity. Before any study-specific procedures are performed all patients will read and sign the IRB-approved informed consent form.

At least 60 qualified patients in each treatment group will receive randomized and blinded study product. The randomization scheme will be 1:1:1 (Active Treatment A: Active Treatment B: Placebo C). The study products are:

Test: Novexatin® 10% Topical Solution (Taro Pharmaceuticals, USA)

Placebo: Placebo (Vehicle) Topical Solution (Taro Pharmaceuticals, USA)

Patients will be assigned to one of the three treatment groups as outlined below and described in Section 9.4 of this protocol.

Treatment Group A: Test treatment for Days 1 – 56 and Placebo treatment for Days 281 – 336

Treatment Group B: Test treatment for Days 1 – 56 and Days 281 – 336

Treatment Group C: Placebo treatment for Days 1 – 56 and Days 281 – 336

Treatment and study durations will be as follows:

Study Duration: 365 days (52 weeks)

A Randomized, Placebo-Controlled, Double-Blind, Parallel-Group, Multi-Site Phase 2b Clinical Study to Assess the Efficacy, Safety and Tolerability of 8-Week Regimens of Novexatin®, 10% Topical Solution (Taro Pharmaceuticals, USA, Inc.) in Patients with Mild to Moderate Onychomycosis

Patients will undergo evaluation for clinical and mycological cure of onychomycosis at each of the 7 clinic visits. Randomized patients who withdraw from the study will not be replaced. The study will be conducted according to the following schedule:

Visit Schedule:

- **Visit 1:** Days -35 to -1 (Screening)
- **Visit 2:** Day 1 (Baseline and Randomization / 1st Treatment start)
- **Visit 3:** Day 57 ± 4 (1st Treatment completion)
- **Visit 4:** Day 141 ± 7 (Interim)
- **Visit 5:** Day 281 ± 14 (2nd Treatment start)
- **Visit 6:** Day 337 ± 14 (2nd Treatment completion)
- **Visit 7:** Day 365 ± 14 (4 weeks post – treatment)

The primary efficacy endpoint is the proportion of patients in each treatment group with a complete therapeutic cure of onychomycosis of the target toenail assessed at Day 141 and at the last test-of-cure visit at Day 365 following either one 8-week treatment period or two 8-week treatment periods. The safety profile of each treatment group will be evaluated by comparing adverse events, application site reactions, monitoring vital signs and changes in clinical laboratory results obtained throughout the study.

The definitions of efficacy variables are stated below:

- **Complete Therapeutic cure:** Complete Clinical Cure **and** Mycological Cure
- **Complete Clinical Cure:** A patient with 0% nail involvement
- **Mycological Cure:** Negative KOH **and** negative culture for dermatophytes associated with onychomycosis
- **Satisfactory Clinical Cure:** ≤ 5% of the target toenail involvement

9.2 Selection of Study Design

Study product dosing is based on previous clinical studies with Novexatin and doses recommended in Investigator's Brochure. As the product composition (cationic peptide) is not comparable to currently marketed products, the study will be conducted in accordance with FDA advice and further communication regarding this class of drugs, specific recommendations for IND 111292, and input from Taro Pharmaceuticals, USA.

9.3 Selection of Study Population

The study will include patients who are diagnosed with onychomycosis by clinical and also microbiological analysis of samples taken from the toenail. In order to participate in this study, patients must have positive cultures.

The stage of 'mild-moderate' will describe the degree of fungal infection of the toenail, and this will be determined by examination of the appearance of the affected toenail(s). Patients with involvement of more than a single toenail will have evaluation based on both big toenails if a

A Randomized, Placebo-Controlled, Double-Blind, Parallel-Group, Multi-Site Phase 2b Clinical Study to Assess the Efficacy, Safety and Tolerability of 8-Week Regimens of Novexatin®, 10% Topical Solution (Taro Pharmaceuticals, USA, Inc.) in Patients with Mild to Moderate Onychomycosis

bilateral infection is present at screening. At Visit 2, a target toenail will be identified by the investigator and all further evaluations will be based on the target toenail. See Appendix A for target toenail identification.

Patients with concurrent disorders that would increase the risk of study participation or confound the interpretation of results, in the judgment of the Investigator, will not be included in the clinical study.

9.3.1 Inclusion Criteria

1. Male and female patients aged 18 or over.
2. Clinical diagnosis of onychomycosis of the target toenail (defined as one of the infected great toenails).
3. Onset of clinical signs of onychomycosis of the target toenail < 2 years of the screening.
4. Clinical signs and symptoms of onychomycosis, confirmed by positive KOH microscopy of the target toenail.
5. Prior to randomization, a confirmed positive fungal culture, of the target toenail.
6. Mild to moderate severity at Visit 1 as defined by Investigator's estimation of approximately 10% to 35% toenail involvement.
7. At least 5 mm of clear nail on the target toenail between the lunular proximal nail fold and the deepest extend of the onychomycosis.
8. The deepest extend of onychomycosis should not contact the lunula.
9. Besides onychomycosis, patients are in overall good health, or have a condition under stable treatment and are willing to comply with adequate foot care for the duration of the study.
10. Females of childbearing potential must not be pregnant or lactating at baseline (as confirmed by a negative urine pregnancy test with a sensitivity of less than 25 mIU/mL or equivalent units of human chorionic gonadotropin). Women of childbearing potential must agree to the use of a reliable method of contraception (e.g., total abstinence, IUD, a double-barrier method [such as condom plus diaphragm with spermicide], oral, transdermal, injected or implanted non- or hormonal contraceptive), throughout the study. If the female is using a hormonal contraceptive, the same product must be taken for 1 month before baseline and must agree not to replace with some other hormonal contraceptives during the study. A sterile sexual partner is not considered an adequate form of birth control.

All females will be considered to be of childbearing potential unless they:

- Are post-menopausal, defined as women who have been amenorrheic for at least 12 consecutive months, without other known or suspected primary cause.

A Randomized, Placebo-Controlled, Double-Blind, Parallel-Group, Multi-Site Phase 2b Clinical Study to Assess the Efficacy, Safety and Tolerability of 8-Week Regimens of Novexatin®, 10% Topical Solution (Taro Pharmaceuticals, USA, Inc.) in Patients with Mild to Moderate Onychomycosis

- Have been sterilized surgically or who are otherwise proven sterile (i.e., total hysterectomy or bilateral oophorectomy) with surgery at least 4 weeks before baseline. Tubal ligation will not be considered a surgically sterile method.

Female patients of childbearing potential are defined as:

- Women without prior hysterectomy of at least 4 weeks, or who have had any evidence of menses in the past 12 months.
- Females who have been amenorrheic for \geq 12 months, but the amenorrhea is possibly from other causes, including prior chemotherapy, anti-estrogens or ovarian suppression.

11. Signed informed consent form which meets all current ICH/FDA regulations

9.3.2 Exclusion Criteria

1. Patients under 18 years of age.
2. Females who are pregnant, lactating or likely to become pregnant during the study.
3. Patients with proximal onychomycosis, dermatophytomas, fungal spikes, limited lateral onychomycosis, white superficial onychomycosis or significant dystrophy of the target toenail that in the Investigator's opinion would impair the evaluation of onychomycosis.
4. Patient has total dystrophic or proximal subungual onychomycosis of the target toenail.
5. History or current diabetes and/or peripheral vascular disease.
6. Presence of mycotic spikes or patient has exclusively lateral groove involvement of the target toenail.
7. Patients with distal nail plate thickness of the target toenail greater than 3 mm.
8. Patient had no new nail growth requiring nail trimming in the target toenail over the previous 2 months.
9. Previous treatment for onychomycosis of the toenail within the last 12 months that was unresponsive to treatment.
10. Onychomycosis not caused by a dermatophyte (e.g., mold infection, *Candida* spp or bacterial infection).
11. Patients with a history of a trauma involving nail bed of the target toenail before onset of clinical signs of onychomycosis.
12. Patients with any significant active or past medical condition or abnormal laboratory value or who are required to start a medical therapy that in the opinion of the Investigator would make them unsuitable for study participation or compromise patient safety.

A Randomized, Placebo-Controlled, Double-Blind, Parallel-Group, Multi-Site Phase 2b Clinical Study to Assess the Efficacy, Safety and Tolerability of 8-Week Regimens of Novexatin®, 10% Topical Solution (Taro Pharmaceuticals, USA, Inc.) in Patients with Mild to Moderate Onychomycosis

13. Patients who are unable to reach their infected toenails and administer the study product to affected toes.
14. Patients who are likely to apply toenail polish, cosmetic products or undergo professional pedicures during the study.
15. Current or history of psoriasis or Lichen planus within the previous 12 months.
16. Immunocompromised either because of concomitant disease (e.g., HIV), or ongoing treatment (e.g., chemotherapy), including patients with a history of organ transplant and patients on long-term corticosteroid therapy (refer to paragraph 9.3.3 for use of concomitant corticosteroid therapy).
17. Receipt of any drug as part of a research study within 30 days prior to dosing.
18. Use within 4 weeks before baseline of 1) topical antifungal therapies on the feet, 2) immunomodulators or 3) systemic corticosteroids.
19. Use of topical corticosteroids on the feet within 2 weeks before baseline.
20. Use of systemic antifungal agents for the treatment of onychomycosis or any antifungal with known activity against dermatophytes within the previous 24 weeks.
21. Current evidence of drug abuse or history of drug abuse within 1 year before the first dose, including, in the opinion of the Investigator, history of alcohol abuse or active alcoholism.
22. Inability to understand the protocol requirements, instructions, and study-related restrictions, the nature, scope, and possible consequences of the clinical study.
23. Unlikely to comply with the protocol requirements, instructions, and study-related restrictions, such as uncooperative attitude, inability to return for follow-up visits, and improbability of completing the clinical study.
24. Patient is the Investigator or his/her deputies, research assistant, pharmacist, clinical study coordinator, other staff or relative thereof directly involved in the conduct of the clinical study or employed by the clinical site, or a first-degree relative of a site employee.
25. Patients with previous exposure to the study drug, or with known allergy to the drug or any of its components.

9.3.3 Restrictions during the Study

The following concomitant medications will not be allowed during the study and during the specified washout periods before Visit 1:

Restricted medication	Examples (not comprehensive)	Washout
Systemic antifungals	Sporanox®,	24 weeks

A Randomized, Placebo-Controlled, Double-Blind, Parallel-Group, Multi-Site Phase 2b Clinical Study to Assess the Efficacy, Safety and Tolerability of 8-Week Regimens of Novexatin®, 10% Topical Solution (Taro Pharmaceuticals, USA, Inc.) in Patients with Mild to Moderate Onychomycosis

	terbinafine,	
Topical antifungals on feet	Lotrimin®, tea tree oil, crystal violet	4 weeks
Systemic corticosteroids	prednisone, prednisolone	4 weeks
Topical corticosteroids		2 weeks
Immunomodulators	chemotherapy, rheumatoid arthritis drugs	4 weeks

Note: Treatment for tinea pedis or tinea cruris will be allowed during the study, and a topical antifungal medication will be provided to patients as deemed necessary by Investigator.

Occasional short term use of systemic and topical corticosteroids other than the feet is allowed to the extent that, in the opinion of the investigator, does not compromise the study results.

The use of topical corticosteroids on the feet is restricted for the entire study.

The use of intranasal, inhaled or ophthalmic corticosteroids is allowed up to 1 mg/day.

9.3.4 Removal of Patients from the Study

Patients will be advised that they are free to withdraw from the study at any time for any reason or, if necessary, the Investigator may withdraw a patient from the study to protect the health of that patient. A patient may also be withdrawn for not complying with study procedures. The clinical report will include all reasons for early withdrawals.

All patients who are randomized will be included in the safety analysis comparing the test and placebo products. If a patient terminates from the study early, all efforts will be made to complete the patient's end of study visit procedures. For early termination the Investigator shall fully document the reason for early termination. Reasons for early termination may include the following:

- Patient withdrew consent
- Significant adverse event that led the Investigator or patient to withdraw for safety reasons
- Non-compliance with protocol requirements/protocol deviation (e.g., use of restricted medication, not following dosing procedures, failure to make scheduled study visits in a timely fashion). A patient may also be withdrawn by the Investigator if:
 - A protocol deviation or intercurrent illness occurs during the conduct of the clinical study, which, in the clinical judgment of the Investigator or after discussion with the Sponsor, may invalidate the clinical study

A Randomized, Placebo-Controlled, Double-Blind, Parallel-Group, Multi-Site Phase 2b Clinical Study to Assess the Efficacy, Safety and Tolerability of 8-Week Regimens of Novexatin®, 10% Topical Solution (Taro Pharmaceuticals, USA, Inc.) in Patients with Mild to Moderate Onychomycosis

- It is discovered that the patient was included in the clinical study in contradiction to the inclusion and exclusion criteria
- Pregnancy
- Significant worsening of onychomycosis such that the Investigator and/or patient believes it is in the best interest of the patient to withdraw from the study and be provided alternative treatment
- Adverse event: if a patient reports symptoms, which are considered unacceptable by the patient or the Investigator, he/she will be withdrawn from the clinical study. The appropriate AE form in the Case Report Form (CRF) will be completed.
- Participant enrolls in another clinical trial, or is found to have previously enrolled in this clinical trial

All reason(s) for premature withdrawal will be recorded. All patients who withdraw or are withdrawn from the clinical study because of an AE, or clinical laboratory abnormality will be followed up at suitable intervals in order to evaluate the course of the AE or laboratory abnormality and to ensure reversibility or stabilization. The subsequent outcomes of these AEs will be recorded in the patient's source file.

Patients who withdraw or are withdrawn after exposure to study product will not be replaced.

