9.3.5 Early Terminations and Protocol Deviations

The following rules and conventions will be used for patients who terminate from the study early or are dropped from the study because of protocol deviations.

If a patient terminates from the study early, all efforts will be made to complete Visit 7 study procedures.

Any patient who either requests to be dropped from the study because of lack of therapeutic efficacy or is dropped by the Investigator for lack of therapeutic efficacy will automatically be considered a "clinical failure" irrelevant of their target toenail assessment score at the termination visit.

Any patient who uses any protocol restricted medication specifically for the treatment of their infection will be discontinued from further participation in the study and automatically be considered a "clinical failure" irrelevant of their target toenail assessment score at the last visit.

Any patient who uses any protocol restricted medication NOT specifically for the treatment of their onychomycosis will be discontinued from further participation in the study. The patient will be considered a "clinical cure" or "clinical failure" based on the target toenail assessments at the termination visit.

Any patient who is dropped for any other reason, other than those covered above, had a positive baseline culture and makes at least one post-baseline visit where clinical assessments for target toenail are performed and/or a KOH and/or mycological culture result is obtained, will be

A Randomized, Placebo-Controlled, Double-Blind, Parallel-Group, Multi-Site Phase 2b Clinical Study to Assess the Efficacy, Safety and Tolerability of 8-Week Regimens of Novexatin[®], 10% Topical Solution (Taro Pharmaceuticals, USA, Inc.) in Patients with Mild to Moderate Onychomycosis

included in the ITT. Examples would include: failure to use the study products as required by the protocol (see section 9.4.5), patient withdraws consent for continued participation, patient fails to make study visits on a timely basis.

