10.2 Determination of Sample Size

The primary statistical analysis of interest is a comparison of the rates of therapeutic cure (as defined by "clinical cure" AND "mycological cure") of Novexatin® 10% topical solution to the rate of therapeutic cure of placebo in the Intent-to-Treat Population (ITT). The rate of therapeutic cure for the Novexatin® 10% topical solution 8-week regimens is expected to be approximately 49%. The rate of therapeutic cure for placebo is expected to be approximately 21%. Approximately 46 patients in each treatment group in the ITT population will provide over 80% power to show a difference at $p < 0.05$ (two-sided Z test and a pooled response rate for the standard error of the difference in proportions) between each of the active treatment groups and the placebo group. To allow for a 23% drop-out rate, a total of 180 patients will be enrolled in the study, with up to 60 patients in each of the treatment groups.

A Randomized, Placebo-Controlled, Double-Blind, Parallel-Group, Multi-Site Phase 2b Clinical Study to Assess the Efficacy, Safety and Tolerability of 8-Week Regimens of Novexatin®, 10% Topical Solution (Taro Pharmaceuticals, USA, Inc.) in Patients with Mild to Moderate Onychomycosis

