Statistical testing will begin with comparison 1. If statistical significance is attained with comparison 1 ($p < 0.05$), then a claim of superiority for comparison 1 can be made and the next comparison in the hierarchical evaluation scheme can be tested for statistical significance. If statistical significance is not attained for comparison 1 ($p \geq 0.05$), then testing of all subsequent comparisons is stopped. The hierarchical, conditional-stepwise evaluation scheme allows for each comparison to be evaluated at the 5% level, while preserving an overall type I error rate of no more than 5%. For the proportion of patients in each treatment group with a complete and almost complete therapeutic cure, complete and satisfactory clinical cure and mycological cure of onychomycosis of the target toenail, the statistical analysis for superiority will be conducted using two-sided Z-Tests and a pooled response rate for the standard error of the difference in proportions for each comparison of interest. The primary and secondary analyses will be performed using an observed case (OC) analysis in the ITT population. Patients discontinued because of lack of treatment effect will be included in the primary analysis as treatment failures.

The following two sensitivity analyses will also be performed on the primary efficacy endpoint in the hierarchical, conditional-stepwise evaluation scheme:

1. Analysis will be performed also including patients without an assessment at Day 365 \pm 14. Patients with missing data at Day 365 \pm 14 will be considered therapeutic failures.
2. Analysis will be performed also including patients without an assessment at Day 365 \pm 14. Patients in Group C with missing data at Day 365 \pm 14 will be treated as therapeutic successes and patients from the Groups A and B with missing data at Day 365 \pm 14 will be treated as therapeutic failures.

Similar sensitivity analyses will be conducted including patients without an assessment at Day 141 \pm 7 for the 4th comparison in the hierarchical, conditional-stepwise evaluation scheme.

Efficacy results will be used to calculate the sample size for the Phase 3 studies.

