**Novexatin 10% topical solution**

**Protocol / Study No. NVXT 1404/71442603**

**7. STUDY POPULATIONS**

**Intent-to-Treat (ITT) Population**

- All randomized patients who applied at least one dose of assigned study product
- Had a positive mycological culture screening (Visit 1)

The primary analyses will be conducted on the ITT population.

Patients who return randomized product bottles with evidence of intentional tampering or unblinding will be excluded from the ITT population and included in the Safety population.

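### Restricted-medication use requires, and non-compliance or late-found ineligibility permits, exit from the whole study, and no route exists to later test-of-cure assessment in an observed-case analysis

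*Protocol*

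**What the plan says.** **Mandatory exit.** Protocol 9.3.5 states: "Any patient who uses any protocol restricted medication NOT specifically for the treatment of their onychomycosis will be discontinued from further participation in the study". That section also removes patients who use restricted medication to treat the infection and classes them as clinical failures. SAP 8.5 repeats both rules.

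**Permitted exit.** Protocol 9.3.4 states: "A patient may also be withdrawn for not complying with study procedures". It also lets the investigator withdraw a patient for a protocol deviation or intercurrent illness that may invalidate the study, or where "It is discovered that the patient was included in the clinical study in contradiction to the inclusion and exclusion criteria".

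**What is collected at exit.** Protocol 9.3.4 and 9.3.5 ask for every effort to complete the Visit 7 procedures. Under Protocol 9.5.7 these include visual assessment, planimetry, KOH and culture. A patient removed for restricted medication not used for onychomycosis is classed as a clinical cure or failure from the termination visit.

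**Who is analysed, and how.** The ITT population in SAP 7 is "All randomized patients who applied at least one dose of assigned study product", with a positive Visit 1 culture. Evidence of bottle tampering or unblinding excludes a patient. Protocol 10.6 and SAP 8.2.1 make the primary analysis observed case within the ITT population. Withdrawals for lack of effect count as failures.

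**What is absent.** I found no provision for stopping product while continuing to attend Visits 4, 5 and 7. The pregnancy rule in Protocol 9.7.1 stops product, but then calls for the study-discontinuation procedures as well.

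**The concern.** The ITT definition keeps most of these patients in the comparison, but the withdrawal rules stop collection of the outcomes that the comparison needs. Who leaves depends on events after randomisation: taking another medicine, missing doses or visits, or an investigator's judgement. An observed-case analysis then compares, in part, the patients who were allowed to stay.

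The design makes this more awkward. There is a 32-week rest period between the two courses, so a patient can be removed while on no study product. For such a patient the remaining test-of-cure visits are already scheduled, and attending them needs no further treatment.

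A termination-visit status is a weak substitute. It describes the nail on the day of exit, which can be months before Day 365. The rule that uses it assigns only a clinical outcome, whereas complete therapeutic cure also needs mycological cure. Neither document says whether an exit assessment outside the Day 141 ± 7 or Day 365 ± 14 window counts as that visit's observation.

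**Working it through.** **1. What a mid-study exit loses.** Take a patient who uses a restricted medication for another condition on Day 100. The first course ended on Day 56 and the second starts on Day 281, so the patient is off product. Exit is mandatory. An assessment on that day falls 141 − 100 = 41 days before the first primary visit and 365 − 100 = 265 days before the second. A patient who leaves after Visit 4 keeps the Day 141 result and loses only Day 365.

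**2. The plan's own sample size.** Inputs from Protocol 10.2 and 10.6: 49% active, 21% placebo, "two-sided Z test and a pooled response rate for the standard error", two-sided 5%, 46 evaluable per group, 23% drop-out, 60 per group.

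Power = Φ{ [d − 1.96·√(2p̄(1−p̄)/n)] / √[(p₁(1−p₁) + p₂(1−p₂))/n] }, with d = p₁ − p₂ and p̄ = (p₁ + p₂)/2.

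- p̄ = 0.35. At n = 46 the null standard error is √(0.455/46) = 0.0995 and the alternative standard error is √(0.4158/46) = 0.0951.
- Power = Φ[(0.28 − 1.96 × 0.0995)/0.0951] = Φ(0.895) = 81.5%. The plan's statement "Approximately 46 patients in each treatment group in the ITT population will provide over 80% power" reproduces; the smallest n for 80% is 45.
- 46/0.77 = 59.7, rounded up to 60 per group and 180 in total. The budget is therefore 14 lost per arm (14/60 = 23.3%).

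**3. How far missing outcomes can move the result.** Assume that all 14 per arm are missing and that the 46 observed respond at the planned rates.

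| Analysis | Active | Placebo | Difference |
|---|---|---|---|
| Observed case | 49% | 21% | 28 points |
| Sensitivity 1, missing = failure | 46 × 0.49/60 = 37.6% | 46 × 0.21/60 = 16.1% | 21.5 points |
| Sensitivity 2, missing = failure in A and B, success in C | 37.6% | (46 × 0.21 + 14)/60 = 39.4% | −1.9 points |

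Power under sensitivity 1 is about 76%. Under sensitivity 2 the sign reverses.

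**4. What keeping patients would do.** The documents do not say how many of the 14 leave because of these rules. I assume 2, 4 or 6 per arm are kept and show two cases. In the first, kept active-arm patients respond at 49%. In the second, they respond at the placebo rate, so the active rate is (46 × 0.49 + k × 0.21)/(46 + k), where k is the number kept. Placebo stays at 21% in both.

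| Kept per arm | Evaluable | Missing | Power, kept at 49% | Active rate, kept at 21% | Power, kept at 21% |
|---|---|---|---|---|---|
| 0 | 46 | 23.3% | 81.5% | 49.0% | 81.5% |
| 2 | 48 | 20.0% | 83.1% | 47.8% | 80.0% |
| 4 | 50 | 16.7% | 84.6% | 46.8% | 78.6% |
| 6 | 52 | 13.3% | 86.0% | 45.8% | 77.2% |
| 14 (limit) | 60 | 0% | 90.5% | 42.5% | 72.0% |

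Missingness falls in every row. Power may rise or fall. These figures use the Z test of the sample-size section; the SAP replaces it with a site-stratified exact Cochran-Mantel-Haenszel test.

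**The case against.** Four stronger readings are tempting, and the documents do not support them.

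- **That non-compliance or late-found ineligibility ends the study automatically.** It does not. Protocol 9.3.4 says such patients may be withdrawn, and Protocol 9.4.5 and 9.6.11 only label patients non-compliant. Automatic exit applies to restricted medication alone.
- **That outcomes are thrown away.** Every component of the primary endpoint is sought at the exit visit. Medication taken for the infection gives an assigned failure, and other restricted medication gives a termination-visit clinical status. What is not collected is the outcome at the scheduled visit.
- **That both primary results are always lost.** Day 141 is lost only if exit comes before Visit 4.
- **That all these patients remain in the ITT population.** A patient found to lack a positive Visit 1 culture is outside it.

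The restricted-medication trigger is also narrower than it first looks. Protocol 9.3.3 allows treatment of tinea pedis or tinea cruris, occasional short-term corticosteroids subject to conditions, and limited intranasal, inhaled or ophthalmic corticosteroids.

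Power gives no clear support either way. Patients who stopped or deviated may respond less well, and including them can lower it.

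All of this stands. It narrows the point but leaves the gap in place: mandatory exit for one trigger, discretionary exit for the others, no follow-up afterwards, and no rule for using an out-of-window exit assessment.

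**Conclusion.** The point holds as a cheap improvement to design and data handling. It does not show an error in the sample size, which reproduces.

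The rules create avoidable missing or early-dated outcomes in patients who mostly belong to the primary analysis population, and the selection depends on what happens after randomisation. The step 3 figures (differences of 28, 21.5 and −1.9 points) bound the effect of the entire budgeted drop-out, not of these rules alone. They assume that all 14 per arm are missing with no assigned outcome. They show that, at the planned drop-out, the conclusion can turn on how missing outcomes are handled, so each avoidable loss matters.

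The share due to these rules is unknown. With an assumed 2 to 6 patients kept per arm, missingness falls from 23.3% to between 20.0% and 13.3%, while power lies between 77.2% and 86.0%. The case for change rests on reduced bias in the ITT comparison, not on power.

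**What to change.** Leave unchanged who stops product and every other clinical rule. In Protocol 9.3.4 and 9.3.5 and SAP 8.5:

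1. Ask patients who leave treatment for restricted-medication use, non-compliance, protocol deviation or late-found ineligibility to attend the remaining test-of-cure visits (Visits 4, 5 and 7) for the efficacy assessments already scheduled there, unless consent is withdrawn.
2. Where an assessment exists at the actual test-of-cure visit, use it in place of termination-visit status. Keep the existing failure rule for medication used for the infection.
3. State whether an exit assessment outside the window counts as the Day 141 or Day 365 observation.
4. Report product discontinuation and study discontinuation separately in SAP Table II, which now shows a single early-termination category.

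The amendment must also make clear how these patients are handled when second-course product is dispensed at Visit 5. That is for the sponsor's clinicians to settle, and this point takes no position on it.

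**Cost.** A protocol amendment, matching SAP text and one disposition field. A few more patients complete visits that were already scheduled, and some outcomes will be observed after other medication, which can be flagged. Item 1 helps only patients whose visits still lie ahead; items 2 to 4 can be settled at any time before database lock.
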